Clinician recruitment and training. Clinicians will be incentivized to participate in the trial by receiving free training in the PST-PC EBPI, culminating in a certification that can be used for career advancement for these clinical social workers. The training in this EBPI is under consideration to be delivered by the AIMS Center to all clinicians at the BHIP sites within the next several years. The results of the trial will be used to guide the remaining trainings. Six care managers in the BHIP program will be randomized to usual training or training with the use of the smart tools within the CMTS system. We will follow the PST-PC training protocol developed by the AIMS Center, which includes training in basic brief treatment skills, therapeutic elements of the intervention and therapy process. This is followed by simulated case training. Clinicians must pass an introductory session, middle and last session before deploying the intervention with patients. In PST-PC this is determined by obtaining a score of 3 ("satisfactory") or greater on the PST Adherence Scales, which utilizes a Likert-type rating scale (0 = *very poor*, 5 = *very good*). [name] will provide clinician training in PST-PC to all clinicians. Clinicians randomized to the decision support condition will also receive a training manual and in-person training in the use of these tools prior to the initiation of PST-PC training. Once a care manager in either arm of the study is certified to provide PST-PC, they will proceed to the four-month fidelity phase of the trial. Five active patients identified from the existing site registry of each care manager will receive treatment during the trial (30 total).

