Clinician Data Collection. Three types of data will be collected from clinicians: clinician assessment of appropriateness and acceptability, intervention usability, and clinician ability to learn the intervention and maintain competency. To measure **decision support usability**, clinicians will complete the Acceptability of Intervention Measure, Intervention Appropriateness Measure, Feasibility Of Intervention Measure, System Usability, Modified Self-Efficacy Scale, and User Burden Scales, which are core measures for this Center. These scales will be collected through the UWAC data portal after clinicians have completed their intervention with 5 patients. To measure **sustained competency**, clinicians will collect audio recordings of patient sessions for review by experts. [name] will conduct these reviews using the PST Therapist Adherence Scales. Sustained competency will be defined by (1) time to first session rated below average after certification in PST-PC and (2) number of sessions rated as <3 ("satisfactory"). Clinicians will not be given feedback on session performance.

Patient data collection. We will use the UWAC data portal⁴⁹ designed specifically for research on mobile depression interventions to confirm eligibility, complete the consent process, and conduct baseline and outcomes assessment. Patient data will be collect before treatment initiation and after treatment ends. Patients will complete a demographic survey to determine gender, age, ethnicity, income categories, and educational level. Patients will complete a series of brief clinical measures to determine the presence of a depressive disorder and if there are any important comorbidities. The *Sheehan Disability Scale*(SDS)^{50,51} is a brief analog too assess functioning in work, social, and health domains, using visual-spatial, numeric and verbal anchors. The scale has been validated in medical and psychiatric populations with a variety of psychiatric diagnoses.^{50,51} The *9-item Patient Health Questionnaire*⁵² (PHQ-9) consists of 9 DSM depression symptoms and one disability item. It has been found to have excellent sensitivity to change over time (sensitivity = .88, sensitivity = .80).⁵³

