Data Analysis. Aim 3 focuses on pilot feasibility data to inform a larger (future) clinical trial comparing decision support of PST-PC to no decision support. Thus, analyses do not focus on hypothesis-driven inferential statistics but on descriptive statistics, graphical summaries, and basic effect sizes. **H1: Usability.** Differences in clinician reported usability between the two clinician groups will be plotted using a dotplot and tested using a *t*-test using the SUS and UBS as dependent variables. **H2: Fidelity/Competence.** We will compare groups on the proportion of clinicians who reach certification (i.e. score of 3 or greater on treatment competence on at least two sessions). Between treatment differences will be tested with a 2-sample proportion test. (Future analyses with larger sample size will use a generalized linear mixed model approach to account for the nested data.)^{54,55} **H3:**

Patient Reported Outcomes. Histograms and kernel density estimates will be plotted by treatment condition to explore differences on depression outcomes (PHQ-9 total score) and overall daily functioning (SDS). Descriptive statistics (*M* and *SD*) of these outcomes will also be examined by clinician group, using Cohen's *d* as an effect size summary. A *t*-test will be used to examine treatment differences in these patient outcomes. Of ultimate interest is whether the modified treatment (i.e., decision-supported PST-PC vs. unsupported PST-PC) effects patient outcomes through enhanced usability and clinician fidelity. We will use graphical summaries of the data to explore the relationships that are consistent with mediation (e.g., correlation of usability with patient outcomes [b pathway], and treatment differences on patient outcomes with fidelity

partialed out [c' pathway']). The primary focus here is whether the data and relationships appear consistent with mediation, as opposed to a formal test, which will be dramatically under-powered.

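### The only planned H2 test compares certification among six clinicians and has no value if all six certify, as the 30-patient target appears to require; the H2 outcomes defined elsewhere have no analysis

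*Combined protocol and SAP*

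**What the plan says.** - **Endpoint and test.** Data Analysis, H2: "We will compare groups on the proportion of clinicians who reach certification", with certification described there as a "score of 3 or greater on treatment competence on at least two sessions". Then: "Between treatment differences will be tested with a 2-sample proportion test". No variant of the test, alpha or sidedness is given.
- **Number of units.** Clinician recruitment and training: "Six care managers in the BHIP program will be randomized to usual training" or to training with the tools. The allocation ratio is not stated.
- **Gate before patients.** Same section: "Clinicians must pass an introductory session, middle and last session before deploying the intervention with patients", each judged against a score of 3 on a 0 to 5 scale. Then: "Once a care manager in either arm of the study is certified to provide PST-PC, they will proceed to the four-month fidelity phase". Five patients of each care manager are treated, 30 in all. No replacement for a clinician who does not certify is described.
- **H2 as hypothesised.** Aim 3 defines competent delivery by fewer sessions rated below standard and a longer time to the first such session after certification. Clinician Data Collection lists "clinician ability to learn the intervention and maintain competency" among the data to be collected and defines sustained competency by the same two measures.
- **Role of testing.** Data Analysis says that the focus is descriptive, and Power and Sample Size says that the sample size was not set by power.

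**The concern.** Certification is the condition for entering the phase in which patients are treated. A trial that recruits as planned has therefore certified everyone, and the H2 endpoint is then constant across arms. A two-sample z test on a constant has zero difference and zero standard error. H1 has a dotplot and H3 has histograms, means, standard deviations and Cohen's *d*. H2 has nothing beyond this one comparison.

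The two outcomes that H2 itself names can still differ between arms after all six certify, but the Data Analysis section does not mention either. As written, the pilot could reach its target and report nothing on the competence difference it set out to explore.

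**Working it through.** **Inputs.** Six clinicians and five patients each (Clinician recruitment and training). Assumed: a 3 v 3 split, two-sided tests at 0.05, and a common certification probability *p*, independent between clinicians. The documents give no certification rate.

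**Step 1: the plan's own figure.** 6 x 5 = 30, which matches the stated total. With five certified clinicians it is 5 x 5 = 25. So 30 needs all six through the gate.

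**Step 2: does the gate equal the analysed endpoint?** The training section requires three passed sessions. The Data Analysis section requires at least two and does not say which. If the same sessions are scored, three passes imply two, and all six count as certified. If other sessions are meant, the link is not established.

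**Step 3: the test when all six certify.** The difference is 3/3 - 3/3 = 0. The pooled proportion is 6/6 = 1, so SE = sqrt(1 x 0 x (1/3 + 1/3)) = 0 and z = 0/0. The unpooled and continuity-corrected forms fail in the same way, as does any other split of six.

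**Step 4: how likely that is.** P(all six certify) = *p*^6:

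| *p* (assumed) | P(all six) |
|---|---|
| 0.70 | 0.12 |
| 0.80 | 0.26 |
| 0.90 | 0.53 |
| 0.95 | 0.74 |

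The other undefined case, none certified, adds (1 - *p*)^6, which is under 0.001 throughout this range.

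**Step 5: the test when it is defined.** At 3/3 v 0/3 the pooled proportion is 0.5 and SE = sqrt(0.25 x 2/3) = 0.408.

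| Variant | Calculation at 3/3 v 0/3 | p |
|---|---|---|
| Pooled z, uncorrected | 1/0.408 = 2.449 | 0.014 |
| Pooled z, continuity-corrected | (1 - 1/3)/0.408 = 1.633 | 0.1025 |
| Unpooled z | 1/0 | undefined |
| Fisher (conditional) | 2 of 20 allocations | 0.10 |
| Barnard, Boschloo (unconditional exact) | 2 x 0.5^6 = 2/64 | 0.031 |

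At 3/3 v 1/3 the uncorrected pooled z gives 0.083, the corrected z 0.387, Fisher 0.40 and the unpooled z 0.014. In the defined ties (1 v 1 and 2 v 2) all the z forms and Fisher give p = 1.

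**Step 6: type I error at 3 v 3.** The uncorrected pooled z rejects at 0.05 only for 3 v 0 and 0 v 3. The probability of these under a common rate is 2*p*^3(1 - *p*)^3, at most 2/64 = 0.031. The unpooled z rejects in four tables (3 v 1, 1 v 3, 2 v 0, 0 v 2), with a maximum of 12/64 = 0.19. Fisher's smallest attainable p is 0.10, so it never rejects.

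**The case against.** The strongest reply is that this is a pilot. The plan puts description ahead of inference, sets no alpha, attaches no decision to the p-value and leaves mixed modelling to a larger study. With everyone certified, 100% v 100% would simply be reported, and nobody would read a difference into it. That stands as a reason to lower the severity. It does not remove the point: the plan still says that the difference will be tested, and it offers no other H2 comparison.

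A second reply is that the link to 30 patients rests on treating two differently worded definitions of certification as one. That is correct, and the conclusion is conditional on it. The Phase 3 / Aim 3 text also says that each care manager will see 30 patients, which would be 6 x 30 = 180. That conflicts with 30 in total, although either total needs all six clinicians.

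A reader might infer more than the documents support:

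- *That the p-value is wrong, or type I error inflated, whenever the test is defined.* The variant is not named. The pooled z has a size of at most 0.031 at 3 v 3, the corrected form nearly matches Fisher, and ties give p = 1. The value 0.10 is the minimum for Fisher's conditional test, not for every exact test.
- *That repeated attempts push both arms to the ceiling.* The documents do not say whether attempts may be repeated.
- *That first-attempt scores or attempt counts could replace certification at no cost.* The training section describes a pass mark, not retained records of this kind.

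**Conclusion.** The point holds with moderate severity. If the training gate is the certification analysed under H2, full recruitment makes the only H2 test undefined and leaves the endpoint unable to separate the arms. This does not depend on alpha, power or the allocation split. How often it would happen does depend on an unknown rate: 12% to 74% for certification probabilities of 0.7 to 0.95, with clinicians assumed independent.

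The dependence on the variant is secondary. The same six clinicians at 3/3 v 0/3 could yield 0.014, 0.031, about 0.10 or no value. That is a reason to specify or drop the test, not evidence of false positives: the pooled form at 3 v 3 is not anti-conservative.

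The more useful finding is that the outcomes by which Aim 3 and Clinician Data Collection define H2 have no analysis, although they can vary after every clinician has certified.

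**What to change.** 1. Drop the proportion test. Report certification as counts per arm (x/3 v y/3). An exact p-value or interval is optional; if Fisher's test is used, note that it cannot go below 0.10 at 3 v 3.
2. Make the H2 analysis the two outcomes already defined: the number of sessions rated under 3, and the time to the first such session after certification. Summarise each per clinician and show it as a six-point dotplot by arm, with the mean difference. Give the number of sessions reviewed beside each count. Mark a clinician with no such session as censored, and do not average that time as if it had been observed.
3. State that these outcomes exist only for certified clinicians, so they are read beside the certification counts.
4. Reconcile the certification definition (three sessions in the training section, at least two in Data Analysis), the patient count (30 per care manager in the Phase 3 text, 30 in total in the training section) and the threshold for a poor session (below standard in Aim 3; below average for the time and under 3 for the count in Clinician Data Collection). State the allocation ratio.

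**Cost.** SAP wording and a little analysis of session ratings that are already planned. No extra participants are needed. Any Fisher p-value will be less favourable than the uncorrected pooled z would have given.

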Aim 3: Test Phase (18 months) In the second to third year of the proposed project we will test the decision-support tools in a small pilot trial with six providers and thirty patients randomized to the use of the decision support tools. **H1:** Clinicians with access to decision tools will report better acceptability, usability, and less burden when using PST-PC than clinicians without the tools (Acceptability of Intervention Measure, Intervention Appropriateness Measure, Feasibility Of Intervention Measure, System Usability, Modified Self-Efficacy Scale, and User Burden Scales). **H2:** Clinicians randomized to decision support tools will more competently deliver EBPI elements (fewer number of sessions rated below standard by experts and more time to first session rated below standard after certification) than clinicians randomized to unsupported EBPI. **H3:** Patients treated by clinicians with access to decision tools will have better patient-reported outcomes than patients treated by clinicians without access to these tools as assessed with functional disability (Sheehan Disability Scale) and change in depression symptoms over time (PHQ-9). We will conduct preliminary analysis to determine if change in clinical outcomes is mediated by clinician adherence to protocol.

Exploratory Aim: Use the data collected during Aims 1-3 to demonstrate proof-of-concept work on using machine learning and natural language processing to automate and potentially personalize decision support tools.

This study addresses IOM Recommendation 6-3: Conduct research to design and evaluate strategies that can influence the quality of psychosocial interventions, and NIMH SP 4.3 Develop innovative service delivery models to improve dramatically the outcomes of mental health services received in diverse communities and populations

SIGNIFICANCE

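### H3 does not say whether PHQ-9 is analysed as a post-treatment or a change score, and leaves the collected baseline unused; define the form and add a baseline-adjusted difference

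*Combined protocol and SAP*

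**What the plan says.** Under Aim 3, H3 names the patient outcomes as "functional disability (Sheehan Disability Scale) and change in depression symptoms over time (PHQ-9". Depression is thus worded as change; disability is not.

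The H3 part of Data Analysis plans histograms and density plots by arm to "explore differences on depression outcomes (PHQ-9 total score) and overall daily functioning (SDS", then means, SDs and Cohen's d. It adds a t-test that "will be used to examine treatment differences in these patient outcomes". It gives no time point, no change-score definition and no baseline covariate. The only variable partialled out is fidelity, in the mediation exploration.

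Under Patient data collection, "Patient data will be collect before treatment initiation and after treatment ends". A baseline value of each scale will therefore exist, and post-treatment is the only possible outcome visit.

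On design, "Six care managers in the BHIP program will be randomized to usual training or training with the use of the smart tools", and "Five active patients identified from the existing site registry of each care manager will receive treatment during the trial (30 total". Patient eligibility limits PHQ-9 at entry to 10-20. Data Analysis opens by saying that "analyses do not focus on hypothesis-driven inferential statistics but on descriptive statistics, graphical summaries, and basic effect sizes".

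**The concern.** Two analysts could both follow the H3 text and report different effect sizes, one from post-treatment totals and one from change scores. The readings agree only if the arms happen to match at baseline. If they do not, raw totals carry part of the gap into d. A change score over-corrects unless the slope of post-treatment on baseline score is near 1.

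Effect sizes are a named output of a pilot meant to inform a larger trial, so it matters which d is reported, and the choice should be fixed before outcomes are seen. For SDS the hypothesis is not worded as change, so the only point there is that an available baseline could sharpen the estimate.

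**Working it through.** **Inputs from the documents.** 6 care managers x 5 patients = 30, which matches the stated total. (The opening of Phase 3 says each care manager will see 30 patients; Aim 3, Study Overview and the training section all give 30 overall, which is used here.) Entry PHQ-9 is 10-20.

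**Assumed, because the documents give no values.** 3 v 3 care managers (15 v 15 patients), complete data, baseline-outcome correlation r of 0 to 0.6, ICC 0.05-0.10, and equal baseline and post-treatment SDs unless stated. Two cases are simulated: (A) care-manager-level baseline and outcome effects correlate like patient-level ones; (B) they do not correlate.

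**1. Chance baseline gap.** SE = sqrt[(2/15)(1 + 4 x ICC)], which is sqrt(0.160) = 0.400 SD at ICC 0.05 and sqrt(0.187) = 0.432 SD at ICC 0.10. The chance of a gap above 0.5 SD in either direction is 0.21 and 0.25.

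**2. What each reading does with it.** Take r = 0.5, a true difference of 0.50 SD and a tool-arm baseline higher by more than 0.5 SD (mean gap about 0.7).
- Case A: raw totals give about 0.50 + 0.5 x 0.7 = 0.85, the change score about 0.50 - 0.5 x 0.7 = 0.15, and the baseline-adjusted difference 0.50.
- Case B, raw/change/adjusted: 0.77/0.08/0.44 at ICC 0.05 and 0.72/0.01/0.39 at ICC 0.10. Adjustment removes the gap fully only under A.

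**3. Variance, adjusted against raw totals.** Under A the ratio is close to (1 - r^2)(1 + 1/26).
- r = 0.5: 0.75 x 1.038 = 0.78, or -22%. Simulated variances at ICC 0.05 are raw 0.160, change 0.160, adjusted 0.125.
- r = 0: 1.038, or about +4%.
- Break-even: r^2 = 1/27, so r is about 0.2.
- Case B at r = 0.5, simulated: 0.160 to 0.141 (-12%) at ICC 0.05 and 0.187 to 0.177 (-5%) at ICC 0.10. Break-even moves up to about r = 0.3 at ICC 0.10.

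**4. Effect of the entry range.** If it shrinks the baseline SD to u = 0.6-0.8 of its unrestricted value, r' = ru/sqrt(1 - r^2 + r^2u^2). With r = 0.5 this gives 0.30/sqrt(0.84) = 0.33 and 0.40/sqrt(0.91) = 0.42. The change in variance is then -7% to -14% under A and 0% to -7% under B.

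**5. Adjusted against change score (r 0.2-0.6).** The adjusted variance is 17-41% lower with equal SDs. With a baseline/post SD ratio of 0.6 it runs from 15% lower to 4% higher, and the change score wins slightly at r of about 0.5-0.6. That ratio is plausible for PHQ-9: a uniform spread over 10-20 has SD 3.16, and 3.16/0.6 = 5.3 points post-treatment.

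**6. One coefficient for both wordings.** If post = a + t x arm + b x baseline, then post - baseline = a + t x arm + (b - 1) x baseline. The arm effect t is identical.

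**7. Scaling d.** With 15 v 15 independent patients and r = 0.5, the sampling SD of d falls from 0.378 to 0.335 if the adjusted difference is divided by the unadjusted post-treatment SD. Divided by the residual SD it is 0.386, so the gain is lost.

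**8. Intervals at r = 0.5.** Patient-level 95% intervals from the adjusted model cover 88-93%, with half-width 0.65-0.66 SD. Comparing six care-manager means on 4 df covers about 94%. Its average unadjusted half-width is 2.776 x 0.940 x 0.400 = 1.04 SD at ICC 0.05 and 2.776 x 0.940 x 0.432 = 1.13 SD at ICC 0.10 (t quantile x expected sample SD over true SD x SE). Adjusted, it is 0.88-1.04 SD across both ICCs and both cases.

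**The case against.** The strongest reply is that this is a 30-patient descriptive pilot. Power and Sample Size says it was not sized for testing, no decision rule in the documents uses d, and a t-test with Cohen's d is a legitimate summary. That stands, and it keeps the point minor. A descriptive d still needs a defined outcome.

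A reader might infer that Aim 3 and Data Analysis contradict each other. The text does not support this: a total score names how the scale is scored, and change in the total score is a possible reading.

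A reader might also infer that adding an adjusted estimate settles the matter. It does not define the planned mean, SD, d and t-test; only a sentence stating the form does. The authors may choose either form.

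The magnitudes all rest on assumed r, ICC, SD ratio and allocation, and on complete data, although attrition is expected. For PHQ-9 the likely gain is small. Those objections stand.

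Finally, clustering is a separate matter that the plan defers under H2: "Future analyses with larger sample size will use a generalized linear mixed model approach to account for the nested data". No interval for d is planned, so the interval advice applies only if one is reported.

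**Conclusion.** The point holds as a cheap improvement. The PHQ-9 outcome form in H3 is unspecified and the collected baseline is unused; for SDS the point is precision only.

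The gain depends on r. Variance is about 22% lower at r = 0.5 if care-manager-level effects correlate alike, 5-12% lower if they do not, about 0-14% lower at r of 0.33-0.42, and up to 4% higher at r = 0. An interval near plus or minus 1 SD remains with or without adjustment.

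A reader might infer that randomisation leaves only random error at stake. The documents do not establish that. Care managers are randomised before training, patients are then drawn from their registries once certification is reached, and no concealment of arm from those recruiting is described. Differential recruitment cannot be excluded. Nor do the documents show that it will occur. It is a further reason to show and adjust for baseline, though adjustment addresses only differences that the baseline score captures.

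**What to change.** In the H3 part of Data Analysis:
- State whether the planned mean, SD, d and t-test use the post-treatment or the change score, and reconcile this with the wording of H3 under Aim 3.
- Show baseline mean and SD of each scale by arm.
- Keep the planned plots and summaries. Beside them, report for each scale the arm difference from one model of post-treatment score on arm and that scale's baseline. Define the adjusted d as this difference divided by the unadjusted pooled post-treatment SD.
- If an interval is given, either label a patient-level one as ignoring care-manager clustering, and so too narrow when the ICC is above zero, or use a clinician-level one. For the latter, take the six care-manager means of post - b x baseline, with b the fitted slope, and compare 3 v 3 by t on 4 df.

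The adjusted model needs no advance guess of r or the SD ratio, which is the reason to prefer it to a plain change-score test. The cost is a few SAP sentences, one model degree of freedom and a slight loss of precision if r is below about 0.2-0.3. No new data are needed.

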Once a set of sufficiently advanced prototypes have been developed, we will move to the *Build* phase of the project. If the solution is a CDSS, at this point the CMTS developer team will be brought into the design process and the tools and desired functionalities will be described until it is clear to all parties. Feedback on the capacity of the CMTS system to accommodate specific designs will be reviewed. When an adequate agreement on the nature of the designs is achieved, the CMTS development team will build the proposed tools in a development environment. Whatever the solution is, a final prototype will undergo initial feasibility evaluation in pilot field deployments with [name]. He will test the system with one or two clinicians in the BHIP program using the prototype with test patient scenarios. Once we have completed the design of PST-PC support system so that it (1) meets needs of its clinicians (i.e., is useful), and (2) is easy to use and understand (i.e., is usable), we will move to the *Test* phase of this study. Data from this process will be used to inform the Matrix of EBPI Modifications.

Phase 3 / Aim 3: Test Phase (18 months). We will conduct a pilot study comparing clinicians randomized to decision support to clinicians randomized to no support. Six care managers who will each see 30 patients will be identified and complete informed consent. Clinicians at all 13 BHIP sites will be offered the opportunity to participate in the trial.

Patient eligibility. Patient participants will be identified through clinic electronic health records. Participants must be 18 years old or older and suffering from depression (score between 10 and 20 on the PHQ-9). Methods Core research assistants will contact potentially eligible patients to conduct a preliminary screening for eligibility, provide a brief description of the study, and obtain informed consent.

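### The H3 t-test on PHQ-9 and SDS, read at patient level, ignores that six clinicians are the randomised units, so its false-positive rate exceeds 5% under any positive within-clinician correlation

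*Combined protocol and SAP*

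**What the plan says.** Phase 3 / Aim 3: Test Phase describes a pilot "comparing clinicians randomized to decision support to clinicians randomized to no support". Clinician recruitment and training repeats the unit: "Six care managers in the BHIP program will be randomized to usual training or training with the use of the smart tools". It also gives the cluster size: "Five active patients identified from the existing site registry of each care manager will receive treatment during the trial (30 total").

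For H3, the Data Analysis section plans histograms, density plots, means and SDs, and Cohen's d. It then says that a t-test "will be used to examine treatment differences in these patient outcomes". It does not say whether the test is run on patients or on clinicians, and it states no alpha level.

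Nesting is mentioned once, in a parenthesis under H2: "Future analyses with larger sample size will use a generalized linear mixed model approach to account for the nested data". Nothing comparable is said for H3.

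The same section opens by limiting its ambition: "analyses do not focus on hypothesis-driven inferential statistics but on descriptive statistics, graphical summaries, and basic effect sizes". Power and Sample Size adds that the numbers were set for practical reasons and not to power hypothesis tests.

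The documents are not consistent on counts. Phase 3 / Aim 3 says "Six care managers who will each see 30 patients will be identified and complete informed consent", which conflicts with five each. Aim 3 in the Specific Aims can also be read as if patients, not only providers, were randomised.

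**The concern.** When clinicians are randomised, the evidence about the treatment effect comes from six independent units. Five patients of the same clinician share that clinician's skill, site and registry, so their scores may be correlated. A t-test on 30 patients counts them as 30 independent observations and understates the standard error.

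The plan itself gives reason to expect such correlation. Its proposed mechanism is that decision support improves clinician competency, which in turn improves patient outcomes, and it intends to relate patient outcomes to clinician usability and fidelity. A model in which the clinician drives the outcome sits badly with treating one clinician's patients as independent.

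The H3 t-test is the only inferential result planned for patient outcomes. The pilot is meant to inform a larger trial, and Clinician recruitment and training says "The results of the trial will be used to guide the remaining trainings". A p-value that is too small could be taken as an early signal of patient benefit.

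**Working it through.** **Inputs from the documents.** Six randomised clinicians with five patients each (Clinician recruitment and training). The plan's own total reproduces: 6 × 5 = 30. There is no stated power, alpha or error rate to reproduce.

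**Assumptions, because the documents are silent.** Two-sided 5% level; 3 v 3 clinicians; normal random-intercept model with total variance 1; ICC ρ from 0 to 0.20.

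**Patient-level t-test.** With m = 5 patients per clinician, the design effect is 1 + (m − 1)ρ = 1 + 4ρ. Under no treatment effect:

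- the difference in arm means is N(0, (2/15)(1 + 4ρ));
- the pooled sum of squares is (1 + 4ρ)·χ²(4) + (1 − ρ)·χ²(24);
- the test takes the squared standard error to be (2/15) × (pooled sum of squares / 28) and rejects when |T| exceeds the 97.5% point of t with 28 df.

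The numerator variance grows by the full design effect. The expected pooled variance is [4(1 + 4ρ) + 24(1 − ρ)]/28 = 1 − 4ρ/14, which falls slightly. Both changes push the test towards rejecting. Numerical integration gives:

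| ICC | Design effect | Effective N (30 / design effect) | True type I error |
|---|---|---|---|
| 0 | 1.00 | 30.0 | 5.0% |
| 0.01 | 1.04 | 28.8 | 5.5% |
| 0.02 | 1.08 | 27.8 | 5.9% |
| 0.05 | 1.20 | 25.0 | 7.4% |
| 0.10 | 1.40 | 21.4 | 9.9% |
| 0.20 | 1.80 | 16.7 | 15.1% |

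A hand check with the normal approximation 2[1 − Φ(1.96/√(1 + 4ρ))] gives 7.4%, 9.8% and 14.4% at ICC 0.05, 0.10 and 0.20. Simulation with 400,000 trials per ICC agrees with the table (7.5%, 10.0% and 15.1% at those three values).

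**Arm split.** With equal cluster sizes a 2 v 4 split has the same type I error as 3 v 3, because the design effect and the distribution of the pooled sum of squares do not change.

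**Cluster size.** If 30 patients per care manager were taken literally (6 × 30 = 180), the error would be 8.5%, 21.3%, 32.7% and 46.6% at ICC 0.01, 0.05, 0.10 and 0.20. The inconsistency in counts therefore matters.

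**Six-mean t-test.** Comparing three clinician means with three (4 df, critical value 2.776) gives 5.0% to 5.1% in simulation at every ICC tried.

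**Effect size.** The pooled SD shrinks on average by √(1 − 4ρ/14) = 0.993, 0.986 and 0.971 at ICC 0.05, 0.10 and 0.20. Cohen's d is therefore inflated by about 0.7%, 1.5% and 3.0%.

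**Precision and power of the alternative.**

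- 95% half-width, patient level, ICC 0: 2.048 × √(2/15) = 0.75 SD.
- 95% half-width, six means, ICC 0: 2.776 × √(2/15) = 1.01 SD.
- 95% half-width, six means, ICC 0.05: 2.776 × √(2/15 × 1.2) = 1.11 SD.
- Rejection rate at a true difference of 0.8 SD and ICC 0.05: 34% for the six-mean test, 56% for the patient-level test.

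**Estimating the ICC from this pilot.** The within-arm ANOVA estimate is (F − 1)/(F + 4), where F is distributed as [(1 + 4ρ)/(1 − ρ)]·F(4, 24). At a true ICC of 0.05 its central 95% range is about −0.21 to 0.40, and it is negative in 46% of trials.

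**The case against.** The strongest reply is that the plan has already limited the weight of this p-value. It says the analyses are mainly descriptive, the sample was not sized for testing, and no alpha, interval or decision rule is attached. The quantity the future trial would most use from H3 is the effect size, which barely moves. The sentence about guiding the remaining trainings refers to the trial's results in general and does not mention H3. All of this stands, and it bounds the consequence.

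The size of the fault also depends on things not stated. The unit of the t-test is an inference, though the natural one for patient scores. The ICC is unknown, and at 0.01 to 0.02 the inflation is trivial. Nothing in the documents favours 0.10 to 0.20 over those lower values. This stands too, and is why a range is given.

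The remark on nesting could be read as a deliberate deferral covering every pilot analysis. Six clusters are a fair reason not to fit a mixed model. They are not a reason to ignore clustering, because a t-test on clinician means needs no mixed model and keeps its level at this size.

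The replacement test is weak: even at ICC 0 its power at 0.8 SD is 39%, against 56% at patient level. That is true, and it is an argument for dropping the p-value rather than keeping one that is miscalibrated. The plan already declines a formal mediation test for lack of power.

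On counts, Study Overview (six care managers, 30 patients) and Clinician Data Collection (five patients per clinician) support five each. The sentence in Phase 3 / Aim 3 is therefore the outlier and looks like a drafting slip. H2 in the Specific Aims also refers to clinicians as randomised.

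**Conclusion.** The concern holds. On the natural patient-level reading, the H3 t-test ignores the unit of randomisation and its type I error is above nominal at every positive ICC. Under the assumptions set out in the check, with five patients per clinician, the excess is negligible at an ICC of 0.01 to 0.02 and moderate at 0.05. At 0.10 to 0.20 the error is two to three times nominal. If the test was meant for clinician means, the fault disappears, but the plan does not say so.

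This should be corrected, but its reach is limited. With equal clusters the mean difference is unbiased and Cohen's d is almost unchanged. What is wrong is the p-value, and any interval built on the same standard error.

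**What to change.** State in Data Analysis that the clinician is the randomised unit. Then choose one of two options for H3:

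1. Replace the t-test with a two-sample t-test on the six clinician means (4 df) for PHQ-9 and SDS.
2. Drop the H3 p-value and report Cohen's d with a plot of the six clinician means by arm.

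If an interval is added under either option, base it on the clinician level. Report between- and within-clinician variance descriptively only, with a note that six clusters estimate the ICC too imprecisely to plan from.

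Reconcile Aim 3 in the Specific Aims, Phase 3 / Aim 3: Test Phase, and Clinician recruitment and training on who is randomised and how many patients each care manager treats.

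The cost is a sentence or two and a few lines of code, with no change to design or data. Option 1 loses power and apparent precision, mostly because only 4 df are available: at patient level and ICC 0 the half-width is 0.75 SD, moving to six means raises it to 1.01 SD, and clustering at ICC 0.05 adds only a further 0.10 SD (1.11 SD). Option 2 avoids the power loss and fits the plan's stated descriptive purpose.
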